3.3.2 Primary Analysis

Repeated Measures ANOVA will be used to detect significant effects with amplification-only and amplification+noiser as fixed effects variables, and participants as a random effects variable. Post-hoc pairwise t-tests will identify further differences.

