1.2 Primary and Secondary Objectives

The primary objective of this study is to evaluate the clinical benefit of a noiser feature for tinnitus relief in 30 participants with mild to moderate sensorineural hearing loss and chronic bothersome tinnitus.

2 Design of the clinical investigation

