2.1 General

2.1.1 Design Type

This is a randomized, cross-over confirmatory study with participants serving as self-controls. Tinnitus Functional Index questionnaire (TFI) will be the outcome measurer, administered at baseline (before study intervention), and after each study condition. Baseline TFI will be compared to that after each study condition.

There are two intervention conditions (duration of 4 weeks each): amplification-only, and amplification+noiser, followed by the same period (4 weeks) of intervention withdrawal.

The outcome measurer (TFI) will be administered before and after each study condition.

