2.2 Procedures

2.2.1 Investigation-related Procedure

Participants will be recruited from the overall population based on their hearing loss and tinnitus intrusion levels; Inclusion criteria include: mild to moderate sensorineural hearing loss, chronic (3+months) bothersome tinnitus (determined by TFI equal or greater than 20 points at baseline), confirmed tinnitus stability with 2 consecutive TFI measures of at least 2 weeks apart, minimum age of 18 years old, no previous experience with hearing aid amplification. Participants will undergo a screening session to confirm study eligibility.

Participants will sign the consent form and complete the demographic questionnaire prior to being assigned randomly to their first intervention condition with a hearing aid fitting (with or without a masking noiser).

Visit 1: hearing screening, demographic information collection, first TFI screening.

Visit 2: between 2 and 4 weeks after the 1st visit, to verify tinnitus stability (via 2nd TFI measurement). If TFI confirms stable Tinnitus condition, participant will be randomly assigned to one intervention condition and can be fit with hearing aids on the same session.

Visit 3: TFI administration, and second intervention condition set up

Visit 4: TFI administration and devices will be returned

Visit 5: TFI administration

3 Statistical design and analysis

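### The primary model of this two-period crossover has no period term, which costs power at balanced sequences and biases the noiser contrast at unequal ones

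*Combined protocol and SAP*

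**What the plan says.** Section 2.1.1 sets out the design: "This is a randomized, cross-over confirmatory study with participants serving as self-controls". The conditions are "amplification-only, and amplification+noiser, followed by the same period (4 weeks) of intervention withdrawal", so the only withdrawal phase follows both conditions. Section 2.2.1 leaves no gap between them: "Visit 3: TFI administration, and second intervention condition set up". The same section requires "no previous experience with hearing aid amplification". It says the first condition is assigned at random, but gives no ratio, blocking or other means of balancing the two orders.

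The objective in section 1.2 is to "evaluate the clinical benefit of a noiser feature for tinnitus relief in 30 participants". The primary analysis in section 3.3.2 is a repeated measures ANOVA with "amplification-only and amplification+noiser as fixed effects variables, and participants as a random effects variable", followed by pairwise t-tests. Neither period nor order is mentioned anywhere. Section 2.1.1 also plans that "Baseline TFI will be compared to that after each study condition".

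**The concern.** Only the contrast between the two conditions separates the noiser from amplification, because both conditions amplify. The TFI scores in that contrast are taken after about 4 weeks of first-ever amplification (Visit 3) and about 8 weeks (Visit 4), whatever the order. If tinnitus keeps changing with longer hearing aid use, the Visit 4 scores differ from the Visit 3 scores for a reason unrelated to the noiser.

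A model with condition and participant alone cannot attribute that change to period. It stays in the residual and weakens the test. If one order has more participants than the other, by chance or through dropout, part of it is also counted as noiser effect. The benefit is then over- or understated according to which order is larger.

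**Working it through.** **Inputs from the documents:** N=30 (section 3.1, given without a derivation, so there is no planned power to reproduce); two conditions back to back; model terms as in section 3.3.2.

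**Assumptions, none in the documents:** SD of the within-participant difference 15 TFI points (10 and 20 also tried); noiser effect τ=8; period effect π from 0 to 10; two-sided alpha 0.05. Signs are set so that positive means improvement.

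**Algebra for complete pairs.** Let d be the improvement under amplification+noiser minus that under amplification-only, n1 the number with amplification-only first and n2 the number with the noiser first.

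- E[d] = τ+π in the n1 group and τ−π in the n2 group.
- Without a period term the estimate has mean τ + π(n1−n2)/N.
- The residual variance is multiplied by 1 + (π²/SD²)·4·n1·n2/(N(N−1)), which at 15/15 is 1 + (π²/SD²)·30/29.
- With a period term the estimate is the average of the two sequence means, in which π cancels at any split.

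The shift is the same if baseline is added to the ANOVA as a third level.

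**Balanced, 15/15.** The shift is zero. For π=8 the variance factor is 1 + (64/225)(30/29) = 1.29. Power is simulated: as written, a one-sample t-test on d with 29 df; with the term, pooled within-sequence variance with 28 df.

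| π | Variance factor | Power as written | Power with term | Type I error as written |
|---|---|---|---|---|
| 0 | 1.00 | 80.6% | 80.5% | 0.050 |
| 3 | 1.04 | 79.5% | 80.5% | 0.045 |
| 5 | 1.11 | 77.4% | 80.5% | 0.038 |
| 8 | 1.29 | 72.2% | 80.5% | 0.027 |
| 10 | 1.46 | 67.3% | 80.5% | 0.019 |

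At π=8, power as written against with the term is 95.4% against 98.8% for SD 10, and 50.0% against 56.2% for SD 20.

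**Unequal splits, π=8.**

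- 18/12: shift 8×6/30 = 1.6, so a true 8 is estimated as 9.6, or 6.4 if the larger group is the other order. Type I error is 0.053.
- 20/10: shift 8×10/30 = 2.7, giving 10.7 or 5.3. Type I error is 0.106.
- When the larger group is the noiser-first order, power as written falls to 51.5% (12/18) and 37.7% (10/20), against 78.9% and 75.8% with the term.
- Dropout from one order of 15/15, complete pairs only: 15/12 gives 3/27 = 11% of π (0.9 points); 15/10 gives 5/25 = 20% (1.6 points).

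With the period term the estimate is 8 and type I error about 0.05 at each of the 30-participant splits.

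**How often such splits occur.** If randomisation is simple and 1:1 (not stated), the binomial(30, 0.5) gives exactly 15/15 in 14.4% of trials, 18/12 or worse in 36.2% and 20/10 or worse in 9.9%.

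**Averaged over simple 1:1 randomisation.** Power as written is 80.6%, 79.1%, 76.4%, 70.2% and 65.1% for π = 0, 3, 5, 8 and 10, against 79.1% with the term. Type I error is 0.05 for both.

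**The case against.** The strongest reply is that validity does not fail on average. Over simple 1:1 randomisation the bias is zero and type I error stays at 0.05. At 15/15 the test is conservative, and at 18/12 its error rate is still about nominal. The 0.11 needs a 20/10 split and a period effect as large as the whole assumed noiser effect. On the averaged figures the term loses about 1.5 points of power if there is no period effect, breaks even near 3 points, and gains 9 to 14 points only at period effects of 8 to 10. Eligibility also requires a stable TFI on two measures, which limits spontaneous drift.

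All of this is correct, and it limits the weight of the point. It does not remove it. Stability before fitting says nothing about change caused by longer amplification. The trial will be run once, at one realised split, and zero bias on average does not correct the estimate at that split.

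Two further limits stand. The period term does not deal with unequal carry-over of the noiser, which the missing washout leaves open. Nor does it help the comparisons with baseline, since baseline always comes first. The dropout figures assume one-sided loss and complete pairs; with incomplete pairs in a mixed model the (n1−n2)/N factor is only approximate.

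**Conclusion.** The concern holds. The missing term and the algebra are certain; the practical size is not, because the documents give no SD, noiser effect, period effect or sequence balance. With an SD of 15 and a noiser effect of 8, the balanced-split loss is about 1 point of power at a period effect of 3, 3 points at 5, 8 at 8 and 13 at 10. At unequal splits, 20% (18/12) or 33% (20/10) of the period effect is added to or taken from the noiser estimate. This is a change that should be made because it is cheap and protects the main contrast. It is not a flaw that invalidates the trial.

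**What to change.** In section 3.3.2, state that the primary noiser contrast (amplification+noiser minus amplification-only) and its 95% confidence interval come from a linear mixed model of the Visit 3 and Visit 4 TFI, with fixed effects for condition and period and a random participant effect. This also names the primary contrast, which the section leaves open. A sequence term is optional; with complete pairs it does not change the estimate or its standard error. Keep the baseline comparisons of section 2.1.1 as separate analyses, and state as a limitation that the period term does not remove unequal carry-over.

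No new data or visits are needed, since the visit number gives the period. The cost is one residual degree of freedom (29 to 28). If there is in fact no period effect, power falls from 80.6% to 78.9% at 18/12 and to 75.8% at 20/10. If outcome data have already been examined, report this as a labelled adjusted analysis beside the planned one.

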3.1 Determination of Sample Size

We will recruit 30 participants in total;

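### Post-hoc pairwise t-tests in a confirmatory crossover have no stated adjustment, order or F-gate; with three TFI levels the familywise error is about 5% if gated and about 12% if not

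*Combined protocol and SAP*

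**What the plan says.** Section 2.1.1 describes the design thus: "This is a randomized, cross-over confirmatory study with participants serving as self-controls". It also fixes two comparisons: "Baseline TFI will be compared to that after each study condition". The two 4-week device conditions are "followed by the same period (4 weeks) of intervention withdrawal", and section 2.2.1 has a TFI at Visit 5, after the devices have been returned.

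Section 3.3.2 is the whole primary analysis. It opens by naming the omnibus test: "Repeated Measures ANOVA will be used to detect significant effects". The only model terms it lists are the two device conditions and a random participant effect. It then closes with the sentence at issue: "Post-hoc pairwise t-tests will identify further differences".

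Section 3.1 gives only a number: "We will recruit 30 participants in total". The document states no significance level, sidedness, primary contrast, multiplicity method, testing order or list of factor levels. It does not say that the t-tests depend on the ANOVA result, and it does not say that they are run regardless of it.

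**The concern.** Section 1.1 says the data could support claims, so it matters how often the planned tests produce a significant difference that is not there. Section 2.1.1 supplies two contrasts (each device condition against baseline), and the two effects named in 3.3.2 supply a third (noiser against amplification alone). A TFI reduction in any of the three could be presented as clinical benefit. The withdrawal TFI, if it enters the model, raises the number of pairs from three to six.

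The plan leaves open whether the ANOVA acts as a gate and which levels it contains. These two choices move the familywise error by a factor of two or more, and as written they could be made after the results are seen.

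**Working it through.** **The plan's own figure.** The only statistical figure is N = 30. It cannot be reproduced, because no effect size, standard deviation, significance level or power is given. No error rate is stated to check against.

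**Inputs.**
- From the documents: n = 30, all measurements within participant.
- Assumed: two-sided 5% per test, paired t-tests, complete data, normal scores with equal variances, and a common correlation of 0.3, 0.5 or 0.8 between TFI measurements. One case with unequal correlations was added.
- Number of levels: two, three or four, because 3.3.2 does not settle it.

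**Two levels.** If the factor holds only the two named device conditions, there is one pair and no multiplicity.

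**Three levels, no true differences, tests run regardless of F.** Three independent tests would give 1 − 0.95³ = 14.3%. Pairwise contrasts share means and are correlated. The large-sample studentized range tail for three means, at 1.96 × √2, gives 12.2%. Simulation at n = 30 (100,000 runs each) gives:

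| Correlation | Any direction, ungated | Any direction, after significant F | False benefit, ungated | False benefit, after significant F |
|---|---|---|---|---|
| 0.3 | 12.35% | 5.02% | 6.53% | 2.90% |
| 0.5 | 12.43% | 5.03% | 6.70% | 2.90% |
| 0.8 | 12.55% | 4.97% | 6.71% | 2.96% |

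False benefit means TFI significantly lower on a device than at baseline, or lower with the noiser than with amplification alone. A single two-sided 5% test has a false-benefit rate of 2.5%, so the ungated figure is 6.6 / 2.5 = about 2.6 times that.

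The gate also holds when both devices differ equally from baseline: one true null remains, and the error is 5.0%. With unequal correlations (0.4, 0.4, 0.85) and no sphericity correction, the gated rate rises to 6.3%.

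**Only the two baseline comparisons of 2.1.1, ungated.** About 9.2% in either direction and 4.5% to 4.7% for false benefit.

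**Four levels (withdrawal included), six pairs, either direction.**
- No true differences, ungated: 20.3% (studentized range), 20.9% (simulation).
- No true differences, after a significant F: 4.9%.
- Baseline differs, the other three are equal: the F is always significant in the simulated case, three true nulls remain, and the gated error is 12.1%.
- Baseline equals withdrawal and the two device conditions are equal to each other: two true nulls remain, and the gated error is 9.8%. The arithmetic check for two independent contrasts is 1 − 0.95² = 9.75%.

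The last pattern is what one would see if amplification helps, withdrawal reverses it and the noiser adds nothing. One of the two possible false findings is then noiser versus amplification alone, the contrast that bears on the objective in section 1.2.

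**After adjustment.** Testing three pairs at 0.05/3 = 0.0167 gives 4.4% to 4.5% with no true differences; Holm is identical in that case.

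**Power cost of Holm.** Noncentral t, 29 degrees of freedom, noncentrality 0.529 × √30 = 2.897. The 0.529 (in standard deviations of the paired difference) is chosen only because it gives 80% power at 5%.
- Level 0.05, critical value 2.045: power 80%.
- Level 0.0167, critical value 2.541: power 64%.
- Level 0.05/6 = 0.0083, critical value 2.832: power 53%.

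**The case against.** The best defence is that section 3.3.2 puts an omnibus test first and calls the t-tests post-hoc. In ordinary usage that means they follow a significant F. With three levels this is Fisher's protected procedure, which needs no further adjustment: the simulation gives 5.0%, subject to sphericity. The primary model also names only two conditions, and the section does not say that baseline or withdrawal is a level.

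Much of this stands, and it rules out two stronger readings that a reader might infer.

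- *That the plan carries a 12% chance of a false benefit.* The 12% counts significant differences in either direction, including worsening. The false-benefit rate is about 6.6% ungated and about 3% gated.
- *That the tests are unadjusted and the trial has no type I error control.* The document is silent on adjustment; it does not rule it out. On the ordinary reading of post-hoc, three levels are controlled at about 5%.

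The defence does not close the matter. The gate is not written. The F described in 3.3.2, taken literally, compares two device conditions and so does not cover the baseline comparisons promised in 2.1.1; the three-level gate that gives 5% is not the model on the page. If Visit 5 is added, the gate fails in plausible patterns. No passage says that Visit 5 is a level, so the four-level figures are conditional on that reading.

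**Conclusion.** The point holds as a gap in error control whose size depends on how 3.3.2 is read. With three TFI levels, familywise error in either direction lies between about 5% (F-gated) and about 12% (ungated). With withdrawal as a fourth level it is about 21% ungated, and 10% to 12% even with the gate when some means truly differ. If only the two device conditions are compared, there is no multiplicity.

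These figures rest on an assumed two-sided 5% level, 30 complete participants, and equal variances and correlations. The three-level results barely change for correlations from 0.3 to 0.8. This should be corrected because the study is called confirmatory and one addition to 3.3.2 settles it under every reading of the levels.

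**What to change.** In section 3.3.2, list the TFI levels compared and replace the post-hoc sentence with one of the following.

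1. **Holm.** All pairwise contrasts are paired within participant and reported with Holm-adjusted p-values at a two-sided familywise 5%. This controls the error whichever means differ.
2. **Fixed order.** Test amplification+noiser versus amplification-only first, since it answers the noiser objective. Then test the remaining named contrasts in a stated order, each at two-sided 5% and only if the one before it is significant. Everything else is descriptive.

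Either choice takes a sentence or two. Under Holm the smallest of three p-values must be below 0.0167, with the worst-case loss from 80% to about 64% power shown above (about 53% if six pairs are kept, which is a reason to settle the levels first). The fixed order costs the first contrast no power, but later contrasts are lost if an earlier one fails.

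Section 1.1 refers to the study in the past tense. If results have already been seen, a testing order chosen now would carry little weight. Holm-adjusted p-values for all listed pairs can still be reported, labelled as added afterwards.

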3.3.3 Interim Analysis

Within 48 of each intervention condition set up time, and again at 2 weeks after each intervention condition set up, the study team will contact each participant to address any questions or issues they may have, and an office visit will be offered if needed.

4 Informed consent process

4.1 Process for obtaining informed consent

Participants are required to sign a consent form prior to participation in the study. The consent form will be provided at the time of their first appointment. Participants are asked to review the entirety of the form and ask questions about the content in the form, if any. Participants consent by writing their names and signature.
